8.2.6. Pregnancy tests

Subjects who are WOCBP must have a negative serum pregnancy test result at Screening (Visit 1) to continue in the study, and a negative UPT at Baseline (Visit 2) prior to application of study medication. In addition, the investigator or designee will perform a urine pregnancy test for subjects who are WOCBP at monthly visits during the study. The UPT kits provided by the Central lab have a minimum sensitivity of 25-mIU β -HCG/milliliter (mL) of urine. If the result of any post-treatment urine pregnancy test is positive, the subject will be withdrawn from the study and the subject's pregnancy documented and followed.

8.3. Other Assessments

8.3.1. Demographics, Medical History and Vitiligo History

During the screening visit, the investigator or designee will interview each subject to obtain demographic information including date of birth, sex at birth, Fitzpatrick skin type, race and, if appropriate, ethnicity. The investigator or designee will interview each subject to obtain medical history information related to all medical conditions, surgeries and disease states that, at screening: are ongoing, require concomitant therapy or are, in the opinion of the investigator, relevant to the subject's study participation. In addition, the medical history of women who are not of childbearing potential should reflect the reason e.g. post-menopausal for 1 year or greater, bilateral tubal ligation, or hysterectomy. The investigator or designee will also obtain an extensive vitiligo history at screening

9. ADVERSE EVENTS

Adverse events will be monitored throughout the study and reported on the appropriate Aclaris Therapeutics, Inc. AE eCRF.

9.1. Definitions

9.1.1. Adverse events (AE)

An AE is any untoward medical occurrence in a subject administered a study medication(s) and which does not necessarily have a causal relationship with the study medication. An AE can therefore be any unfavorable and unintended sign or symptom associated with the use of a study medication (including an abnormal laboratory finding), whether or not related to the study medication.

Thus, any new, clinically significant worsening of an existing sign, symptom or disease, should be considered an AE.

Every new episode or clinically significant worsening of a chronic condition (e.g., headaches, seasonal allergies, depression, or hypertension) should be reported as a separate AE, even if the condition is reported in the subject's medical history.

The investigator should, when certain, report a diagnosis rather than the signs, symptoms or clinically significant abnormal laboratory values associated with the AE. Otherwise, signs, symptoms or abnormal laboratory values may be used to describe the AE.

Any CS abnormality discovered prior to the first study medication treatment should be reported as medical history, not as an AE.

9.1.2. Serious adverse event (SAE)

A Serious Adverse Event is any untoward medical occurrence that at any dose:

- Results in death
- Is life threatening
- Requires inpatient hospitalization or prolongation of existing hospitalization
- Results in persistent or significant disability/incapacity, or
- Is a congenital anomaly/birth defect
- Is an important medical event.

The term "life threatening" refers to an event in which the subject was at risk of death at the time of event; it does not refer to an event that hypothetically might have caused death if it were more severe.

Inpatient hospitalization is considered to have occurred if the subject is admitted to the hospital on an in-patient basis, even if released the same day. Prolongation of hospitalization is defined as an additional night stay in the hospital. Hospitalization for a diagnostic test (even if related to an AE) or elective hospitalization that was planned before study enrollment (signing the ICF) are not themselves reasons for an event to be defined as a SAE.

Important medical events are those that may not be immediately life threatening, result in death or hospitalization, but are clearly of major clinical significance and may jeopardize the subject or require intervention to prevent one of the outcomes listed in the SAE definition above. These should also usually be considered serious. Examples of such events are intensive treatment in an emergency room or at home for allergic bronchospasm, blood dyscrasia or convulsions that do not result in hospitalization.

9.1.3. Unexpected adverse event

An AE is considered unexpected if it is not listed in the Investigator Brochure or is not listed at the specificity or severity that has been observed.

9.1.4. Adverse event reporting period

The investigator must start reporting non-serious AEs with the subject's first study medication application and continue reporting until the end of the subject's last study visit. Reporting for SAEs must start when the subject signs the ICF and continue until the end of the subject's last visit.

9.1.5. Severity

The investigator is to define the severity of each AE using the following definitions as a guideline. The investigator will consider the range of the possible severity of the event and identify the severity that is the most appropriate according to her/his medical judgment.

Mild – Awareness of signs or symptom, but easily tolerated

Moderate – Discomfort, enough to cause interference with usual activity

Severe – Incapacitating with inability to perform usual activity.

9.1.6. Relationship to study medication

The investigator will determine if there is a reasonable causal relationship between the study medication and an AE or not. The investigator will use her/his best medical judgment and consider all relevant factors (e.g., temporal relationship, location of the event, the subject's relevant medical history, concomitant therapies and concurrent conditions) to determine the relationship of the AE to the study medication. The investigator will define the relationship of an AE to the study medication by selecting one of the following categories:

Related – There is a reasonable causal relationship between the study medication and the AE.

Not Related – There is not a reasonable causal relationship between the study medication and the AE.

The expression “reasonable causal relationship” is meant to convey in general that there are facts (evidence) or arguments to suggest a causal relationship (International Conference on Harmonization [ICH] E2A).

9.2. Reporting Procedures

9.2.1. Procedures for reporting adverse events

At each post-enrollment visit, the investigator will question the subject to elicit AEs using a non-directive question such as “Has there been any change in your health since the previous study visit?” If appropriate, based on the subject’s response to non-directed questioning to elicit AEs, the investigator will follow-up with directed questions and appropriate evaluations.

Any AE noted during the reporting period must be reported in the source documents and on the appropriate AE eCRF. AEs that are defined as “Not Related” to the study medications will be followed until they are resolved or until the subject’s last study visit. AEs that are defined as “Related” to the study medications will be followed until they are resolved or, if not resolved after the subject’s last study visit, until in the opinion of the investigator, the AE reaches a clinically stable outcome with or without sequelae.

9.2.2. Procedure for reporting a serious adverse event

Upon becoming aware of a SAE occurring during the AE reporting period, whether or not related to the study medications, the investigator must:

1. Take the appropriate medical action to ensure the subject’s safety.
Immediately (within 24 hours) inform the Medical Monitor of the SAE by telephone:
[name].
Office [contact]
SAE [contact]
E-mail: [contact]
2. Within 24-hours complete, as fully as possible, an AE eCRF and an SAE form; fax or e-mail the forms and any other relevant information (e.g., concomitant medication eCRF, medical history eCRF, laboratory test results) to the Aclaris Therapeutics, Inc. Medical Monitor.
3. Monitor and document the progress of the SAE until it resolves or, if not resolved after the subject’s last study visit, until in the opinion of the investigator the AE reaches a clinically stable outcome with or without sequelae AND the investigator and Aclaris Therapeutics, Inc. Medical Monitor agree that the SAE is satisfactorily resolved.
4. Inform the Aclaris Therapeutics, Inc. Medical Monitor of SAE updates by telephone followed by an SAE form update sent by e-mail.
5. Comply with the appropriate regulatory requirements and Aclaris Therapeutics, Inc. instructions regarding reporting of the SAE to the responsible Institutional Review Board (IRB) or Ethics Committee (EC).

9.2.3. Safety Monitoring Discontinuation Criteria

Any subject who develops any of the following ECG findings during the active treatment phase will be instructed to stop study medication and will be withdrawn from the study:

- A post-study medication ECG result where the evaluator’s interpretation shows any of the following:

- Clinically significant rhythm disturbance other than sinus rhythm or ectopic supraventricular rhythm (ectopic atrial rhythm)
- Clinically significant conduction disturbance including PR >240msec, pre-excitation (delta wave and PR <120msec), second degree or higher AV block
- New finding of QRS>120ms (if not present at screen. For example, subjects with Right Bundle Branch Block at screening would not need to be withdrawn from the study if their subsequent ECGs remained unchanged).
- Evidence of QT-interval prolongation, defined as an increase in the QTcF interval>60ms from Visit 1
- Acute signs of ischemia or infarction
- Any ECG abnormality which may, in the opinion of the investigator, represent a new medical issue of concern

Site staff must perform protocol-required procedures for trial discontinuation and follow-up.

9.2.4. Study Medication Interruption and Discontinuation Criteria

9.2.4.1 Study Medication Interruption

Treatment with ATI-50002 Topical Solution should be temporarily interrupted in the event of severe adverse events considered related to ATI-50002, or in the event of one or more of the abnormal laboratory values in Table 1.

Table 1: Study Medication Interruption Criteria

Laboratory Test	Hold Study Medication if:	Resume Study Medication if:
WBC count	< 2 x 10 ⁹ /L	≥ 2.5 x 10 ⁹ /L
ANC	< 1 x 10 ⁹ /L	≥ 1.5 x 10 ⁹ /L
Lymphocyte count	< 0.5 x 10 ⁹ /L	≥ 0.75 x 10 ⁹ /L
Platelet count	< 75 x 10 ⁹ /L	≥ 100 x 10 ⁹ /L
Hemoglobin	< 8 g/dL or a decrease > 2g/dL	≥ 10 g/dL
AST or ALT	> 3 x ULN	< 2 x ULN or within 20% of Baseline values
Serum creatinine	>2 x ULN	<1.5 x ULN or within 10% of Baseline value

If a subject has one or more of the abnormal laboratory values noted in Table 1, the investigator or designee upon receipt and review of the central laboratory report should instruct the subject to hold study medication applications. The investigator or designee should ask the subject about symptoms, concomitant illnesses and medications and repeat the test(s) as soon as possible. The Medical Monitor must be notified of dose interruptions due to SAEs considered related to study medication or laboratory abnormalities noted in Table 1.

If the retest confirms the abnormal laboratory value, then the study medication should continue to be held followed by repeat testing once a week or sooner at the discretion of the investigator. The subject should be followed until the laboratory abnormality(s) return to normal or to baseline values.

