7.6. Dose Modification

If the subject experiences application site AE(s), study medication may be stopped for up to a total of 3 days or the frequency of study medication application may be reduced from twice-daily to once-daily for up to a total of 6 days. Dose interruptions must be documented in the source document and eCRF. Dose modifications greater than these must be reviewed and approved by the Medical Monitor. Refer to Section 9.2.4 for Study Medication Interruption or Discontinuation due to related SAEs or specific abnormal laboratory values.

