9.2.4.2 Study Medication Discontinuation

Study medication should be permanently discontinued in the event of any of the following:

- Severe infection requiring parenteral antimicrobial therapy or hospitalization
- Symptomatic herpes zoster
- Malignancy – except for non-melanoma skin cancer (SCC or BCC) not in or near the treatment area
- Anaphylactic or severe allergic reaction
- WBC Count: < 1 x 10⁹/L or second occurrence of < 2 x 10⁹/L
- ANC:< 0.5 x 10⁹/L or second occurrence of < 1 x 10⁹/L
- Lymphocyte count:< 0.3 x 10⁹/L or second occurrence of < 0.5 x 10⁹/L
- Platelet count: < 50 x 10⁹/L or second event of < 75 x 10⁹/L - in each case, value should be confirmed by retesting before treatment discontinuation
- Hemoglobin: < 6.5 g/dL or second occurrence of < 8 g/dL - in each case, value should be confirmed by retesting before treatment discontinuation
- AST or ALT:
 - > 5 x ULN persisting for 2-weeks of study medication interruption or second event of > 5 x ULN
 - > 3 x ULN with total bilirubin >2 x ULN or symptoms of hepatocellular injury [fatigue, nausea, vomiting, right upper quadrant pain or tenderness, fever, rash and/ or eosinophilia (>5%)].

- Serum creatinine: $> 2 \times \text{ULN}$ persisting for >2 weeks of treatment discontinuation or second occurrence of $> 2 \times \text{ULN}$

The continued treatment of subjects who experience other serious or severe adverse events considered related to study treatment should be discussed with the Sponsor's medical monitor.

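### The adverse-event dose hold uses severe and serious inconsistently across Sections 7.6, 9.2.4.1 and 9.2.4.2, leaving the hold, its notification and the rule for severe application-site reactions unclear

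*Combined protocol and SAP*

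**What the plan says.** The protocol separates the two terms. Section 9.1.2 defines a serious event by its outcome: death, threat to life, hospitalization, disability, congenital anomaly, or an important medical event. Section 9.1.5 makes severe the top grade of an intensity scale, for events that incapacitate the subject.

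Four sentences then deal with stopping treatment for a related event:

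- Section 9.2.4.1, hold rule: "Treatment with ATI-50002 Topical Solution should be temporarily interrupted in the event of severe adverse events considered related to ATI-50002".
- Section 9.2.4.1, notification: "The Medical Monitor must be notified of dose interruptions due to SAEs considered related to study medication or laboratory abnormalities noted in Table 1".
- Section 7.6, cross-reference: "Refer to Section 9.2.4 for Study Medication Interruption or Discontinuation due to related SAEs or specific abnormal laboratory values".
- Section 9.2.4.2, closing paragraph: the continued treatment of subjects with "other serious or severe adverse events considered related to study treatment" should be discussed with the medical monitor.

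Section 7.6 also has its own rule for application-site events, with no severity limit: "study medication may be stopped for up to a total of 3 days or the frequency of study medication application may be reduced", the reduction being to once daily for up to 6 days in total. It adds: "Dose modifications greater than these must be reviewed and approved by the Medical Monitor".

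Section 9.2.2 separately requires every SAE, related or not, to be reported to the Medical Monitor within 24 hours.

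**The concern.** A site needs to know which related adverse events call for a hold, and which holds must be notified to the Medical Monitor. The hold sentence and the notification sentence stand in the same subsection and ought to describe the same interruptions, but one is keyed to intensity and the other to seriousness. Because the protocol defines these as separate attributes, a reader cannot treat the words as synonyms.

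The overlap with Section 7.6 matters because the product is a topical applied to the face for up to 48 weeks, so application-site reactions are a foreseeable kind of related event. For a severe one, one section directs an interruption. The other makes a stop optional and allows continued dosing at reduced frequency.

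What is at stake is consistent handling of subjects at about 5 sites, in a study whose primary objective includes safety and tolerability. Two sites, each following the text, could hold or continue treatment for the same related event.

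**Working it through.** No arithmetic applies, and the plan states no figure to reproduce. The check takes each combination of severe and serious, for a related event not already on the permanent-discontinuation list in Section 9.2.4.2, through each passage.

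| Related event | Hold under 9.2.4.1? | Does 7.6 point to 9.2.4 for it? | Notice of the hold mandatory under 9.2.4.1? | Discussion under 9.2.4.2? |
|---|---|---|---|---|
| Severe and serious | Yes | Yes | Yes | Yes |
| Severe, not serious | Yes | No | No | Yes (should) |
| Serious, not severe | No trigger stated | Yes | Yes, if held | Yes (should) |
| Neither | No trigger stated | No | No | No |

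The first and last rows are consistent. The middle two are not.

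**(a) Serious, not severe.** An example is an important medical event graded moderate. Section 9.2.4.1 gives no express reason to hold. The notification sentence and the 7.6 cross-reference both assume that interruptions for related SAEs occur, but the trigger they assume is stated nowhere. Section 9.2.4.2 asks only that continued treatment be discussed.

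**(b) Severe, not serious.** Section 9.2.4.1 directs a hold. Its notification sentence, which is a *must*, does not include that hold. Two other routes to the Medical Monitor remain: the discussion in 9.2.4.2, which is a *should*, and, for application-site events only, the 7.6 approval step once the modification goes beyond 3 days stopped or 6 days at once daily.

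**(c) Severe application-site reaction, related, not serious.** Both sections apply:

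- Section 9.2.4.1 says treatment should be interrupted and sets no duration.
- Section 7.6 says it may be stopped or reduced in frequency, with approval needed beyond its limits.
- A hold of up to 3 days needs neither approval under 7.6 nor mandatory notice under 9.2.4.1. A longer one needs approval under 7.6 but still no notice under 9.2.4.1.
- Neither section says which governs. The 7.6 cross-reference does not settle it, because it sends the reader to 9.2.4 for SAEs and this reaction is not one.

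**Reporting of the event itself.** Under Section 9.2.2 every SAE reaches the Medical Monitor whatever the hold text says. The notification gap is therefore confined to row 2.

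**The case against.** The strongest reply is that only Section 9.2.4.1 states an adverse-event hold trigger, so there are not several competing rules. The 7.6 sentence is a pointer and the notification sentence is a reporting duty; at worst they describe 9.2.4.1 loosely. Section 9.2.4.2 brings both classes to the medical monitor in any case. Section 7.6 can be read as the general rule for application-site events of any grade, with 9.2.4.1 as the specific rule for severe related ones.

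Much of this stands, and it rules out several stronger conclusions that a reader might draw:

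- *Serious events could go unreported.* They could not: Section 9.2.2 covers all of them within 24 hours.
- *Section 7.6 itself holds treatment for related SAEs.* It does not; it refers to 9.2.4 for that.
- *The 3 days in 7.6 cap an interruption that 9.2.4.1 leaves open-ended.* They are the point beyond which the Medical Monitor must approve, not a maximum.
- *There is no route to resuming after an adverse-event hold, because Table 1 covers laboratory values only.* Table 1 is limited in that way, but 9.2.4.2 directs the question of continued treatment to the medical monitor.
- *A hospitalised infection shows the hold gap.* It is a weak example, since severe infections requiring hospitalization are on the permanent-discontinuation list. The gap could arise only for one graded below severe.
- *A planned analysis is compromised.* Section 11.2 names no interruption endpoint and no comparison between sites, and 7.6 requires interruptions to be recorded in the source and the eCRF.

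What the reply does not remove is the mismatch. Reading 7.6 as general and 9.2.4.1 as specific is reasonable, but the protocol does not say so. Section 9.2.4.2 uses a third wording, and its *should* is weaker than the *must* in 9.2.4.1.

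**Conclusion.** The inconsistency is real, is in current body text, and sits in an operative safety rule. It comes to three points:

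- Related serious, non-severe events have no express hold trigger, although two sentences presuppose one.
- Holds for related severe, non-serious events are outside the mandatory notification sentence.
- For severe related application-site reactions, two sections give different instructions and neither is said to govern.

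Two of the four severe/serious combinations are affected. That counts logical categories and does not measure impact; the documents give no event rates, so the number of affected events among 33 subjects cannot be estimated. Sample size, power and the planned descriptive analyses are untouched.

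The conclusion assumes that the terms carry the meanings given in 9.1.2 and 9.1.5, and it covers only events not already requiring permanent discontinuation. It takes no position on which events ought to lead to a hold. The point should be corrected, but it does not undermine the study.

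**What to change.** Reconcile Section 7.6, both sentences of Section 9.2.4.1 and the closing paragraph of Section 9.2.4.2 so that:

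1. one event class, in the terms of 9.1.2 and 9.1.5, is named as the trigger for the adverse-event hold;
2. the same class is named in the sentence requiring the Medical Monitor to be notified of that hold;
3. the 7.6 cross-reference and the closing paragraph of 9.2.4.2 use the same wording;
4. the text says whether 7.6 or 9.2.4.1 governs a severe related application-site reaction.

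The sponsor's medical team must choose the event class and the governing section. The cost is a wording change in an amendment, with no added visit, procedure or data item.

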6.4.2. Visit 2 (Day 1) / Baseline

This visit must occur within 28 days after Visit 1.

Subsequent study visit dates must be scheduled based on the date of Visit 2.

This visit may not occur before the investigator reviews the Visit 1 clinical laboratory test results for all the measured analytes. For the subject to continue in the study all clinical laboratory test results must be within the range of normal for the laboratory or, if there are any abnormal results, they must be defined as not clinically significant (NCS) by the investigator. Subjects with any Screening laboratory values meeting the Study Medication Interruption Criteria found in Table 1 must have repeat lab testing performed with results meeting the minimum criteria for resumption in order to initiate treatment at Baseline (Visit 2). For WOCBP, the serum pregnancy test from Visit 1 must be negative for a subject to continue in the study.

The investigator must review the evaluator's interpretation of each subject's Visit 1 ECG prior to Baseline/Visit 2 and comment on the clinical significance of any result that is defined by the evaluator as abnormal. The subject must not continue in the study and apply study medication, if the Visit 1 ECG meets any of the Criteria in Exclusion Criterion 21.

At this visit, the investigator or designee will perform the following procedures **PRIOR TO APPLICATION OF STUDY MEDICATION:**

1. Query the subject in a non-directive manner about any changes in her/his health since the previous visit and report changes on the appropriate form.
2. Query the subject about any changes in her/his concomitant therapies since the previous visit and report changes on the appropriate form.
3. Confirm the subject continues to comply with all study requirements, is eligible to continue in the study and has followed all study instructions.
4. Confirm the subject meets all inclusion criteria and no exclusion criteria.
5. Confirm Facial vitiligo TBSA is at least 0.25% with at least one area of normal pigmentation on the face.
6. Measure vital signs.
7. Perform a urine pregnancy test for WOCBP; results must be negative for the subject to apply the first dose of study medication.

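### Table 1 gives the haemoglobin hold for a fall of more than 2 g/dL no matching restart condition, so above a Baseline of 12 g/dL one result can meet both Hold and Resume

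*Combined protocol and SAP*

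**What the plan says.** In Section 9.2.4.1, Table 1, the Hold entry for haemoglobin is "< 8 g/dL or a decrease > 2g/dL" and the Resume entry is 10 g/dL or above, with nothing about the size of the fall. The AST/ALT and creatinine rows do refer to Baseline in their Resume entries: "< 2 x ULN or within 20% of Baseline values" and "<1.5 x ULN or within 10% of Baseline value".

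The text below the table adds three rules:

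- On retesting: "If the retest confirms the abnormal laboratory value, then the study medication should continue to be held followed by repeat testing once a week". The investigator may choose a shorter interval.
- On follow-up: "The subject should be followed until the laboratory abnormality(s) return to normal or to baseline values".
- On oversight: "The Medical Monitor must be notified of dose interruptions due to SAEs considered related to study medication or laboratory abnormalities noted in Table 1".

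Section 6.4.2 uses the Resume column for a different purpose. A subject whose screening values meet a hold criterion needs repeat "results meeting the minimum criteria for resumption in order to initiate treatment at Baseline (Visit 2".

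Section 9.2.4.2 sets the permanent stop at "Hemoglobin: < 6.5 g/dL or second occurrence of < 8 g/dL", each confirmed by retest. It has no limb for a fall.

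**The concern.** The haemoglobin row has two ways into a hold and one way out, and the way out fits only the first. A subject held solely because haemoglobin fell by more than 2 g/dL, while still at 10 g/dL or above, meets the Resume entry at the moment the hold begins. If the retest gives the same value, the retest sentence says keep holding, while the Resume column says the restart condition is met.

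The sponsor chose a fall of more than 2 g/dL as a reason to stop the drug. Read literally, the Resume column lets the drug restart while that fall persists. Two sites could act differently on the same result, each relying on Section 9.2.4.1. For a fall that stays at or above 10 g/dL, Table 1 is the only haemoglobin-specific dosing rule, because Section 9.2.4.2 does not address it.

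**Working it through.** The plan states no figure to reproduce here, so the check is whether the two entries can both be true.

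**Inputs.** From Table 1: hold if h < 8 or the fall exceeds 2 g/dL; resume if h ≥ 10. Here h is the result and B the Baseline (Visit 2) value. Two assumptions are needed. First, the fall is B − h. The Hold entry names no reference, and Baseline is the natural reading because two other rows use it. Second, B runs from 11 to 16 g/dL, because the documents give no baseline haemoglobin.

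**Overlap.** The fall limb is met when h < B − 2, and Resume is met when h ≥ 10. Both hold when 10 ≤ h < B − 2, which is possible only if B − 2 > 10, that is B > 12.

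| B (g/dL) | Hold below max(8, B − 2) | Results meeting Hold and Resume | Width, B − 12 | Fall at h = 10, B − 10 |
|---|---|---|---|---|
| 11 | 9 | none | 0 | no overlap |
| 12 | 10 | none | 0 | no overlap |
| 13 | 11 | 10.0 to <11.0 | 1 | 3 |
| 14 | 12 | 10.0 to <12.0 | 2 | 4 |
| 15 | 13 | 10.0 to <13.0 | 3 | 5 |
| 16 | 14 | 10.0 to <14.0 | 4 | 6 |

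Example: B = 14.0 and a retest of 11.5 give a fall of 2.5, which exceeds 2 (Hold), and 11.5 ≥ 10 (Resume).

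**Other rows.** The white cell, neutrophil, lymphocyte and platelet rows cannot overlap, because each Resume threshold lies above its Hold threshold (2.5 v 2, 1.5 v 1, 0.75 v 0.5, 100 v 75, all × 10⁹/L). AST/ALT can overlap only if 1.2 × Baseline > 3 × ULN, so Baseline > 3/1.2 = 2.5 × ULN. Creatinine can overlap only if 1.1 × Baseline > 2 × ULN, so Baseline > 2/1.1 = 1.82 × ULN. Those are unusually high starting values. The haemoglobin overlap needs only B > 12 g/dL.

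**After the fix.** If restart also requires that no hold criterion is still met, the restart level is max(10, B − 2): 10, 10, 11, 12, 13 and 14 for B = 11 to 16. No result then meets both. The gap between restart and hold levels is 10 − 9 = 1 at B = 11, and 0 from B = 12 to 16.

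**The case against.** The strongest reply is that the section already answers the question. A retest between 10 g/dL and B − 2 is still a fall of more than 2 g/dL, so it confirms the abnormal value, and the retest sentence says hold. Section 6.4.2 calls the Resume values minimum criteria, which suggests necessary rather than sufficient. The Medical Monitor hears of every Table 1 interruption. Investigators must judge the clinical significance of each out-of-range result (Section 8.2.4) and may withdraw a subject in that subject's interest (Section 5.9). An absolute floor of 10 g/dL after work-up could also be deliberate, since it avoids repeated switching around B − 2.

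Much of this stands. The protective reading is the better one, and a careful site would probably follow it. But none of these provisions sets the restart rule:

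- The minimum-criteria wording belongs to the screening rule and does not say what else is needed.
- The follow-up sentence governs how long to follow the subject, not when to restart.
- The Medical Monitor is notified; agreement to restart is not required.
- The Medical Monitor approval in Section 7.6 is introduced for application-site events, and that section sends laboratory interruptions back to Section 9.2.4.
- If the 10 g/dL floor is deliberate, the retest sentence contradicts it and needs an exception.

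A reader might go further and infer that the protocol directs restart after falls of 4 to 6 g/dL. It does not. Those figures show only where the Resume entry is already met at B = 14 to 16, and the retest sentence points the other way.

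**Conclusion.** The conflict is real but small. The Resume entry leaves the fall limb without a restart condition, and no text says whether it or the retest sentence prevails. The overlap is [10, B − 2) g/dL for B above 12 g/dL, or 10.0 to <12.0 g/dL at an assumed Baseline of 14.

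The exact bounds rest on measuring the fall from Baseline (Visit 2). A different fixed reference, such as the screening value, would take the place of B and leave the same gap.

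A reader might infer that subjects would go unprotected. The documents do not support that. Under either reading the fall still triggers a hold, questions about symptoms and medications, a prompt retest, Medical Monitor notification, and follow-up to normal or baseline. The overlap lies wholly at or above 10 g/dL. The hold below 8 g/dL, the discontinuation limits and the efficacy analysis are unaffected. The documents give no basis for estimating how often the overlap would occur. This is a minor safety-rule correction, worth making because it is cheap and removes a choice between two stated rules.

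**What to change.** Make two edits in Section 9.2.4.1.

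1. In the haemoglobin Hold cell, write: *a decrease > 2 g/dL from Baseline (Visit 2)*.
2. Add to the retest paragraph: *Study medication is resumed only when the Resume criterion is met and no Table 1 hold criterion is still met, unless the Medical Monitor documents agreement to restart (e.g., a stable fall judged unrelated to study medication).*

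The second edit also settles the AST/ALT and creatinine overlaps, so the Resume cells can stay as they are. The Medical Monitor clause is needed because a subject with a lasting but unrelated fall would otherwise have no route back to treatment.

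The cost is one table cell and one sentence, with no new tests or data. Some holds will be longer. At baselines of 12 g/dL and above there is no gap between the hold and restart levels, so a subject near B − 2 could move between them on measurement noise.
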